5.4 Inclusion/Exclusion Criteria

The study sample will be drawn from a population of Veterans who currently receive VA services and providers in two VA Liver Clinics. Veterans presenting to HCV clinics who report engaging in any level of alcohol use within the prior 30 days will be recruited for the study.

Additional criteria for inclusion include: (a) a liver disease diagnosis, (b) not presently in treatment for a substance use disorder, and (c) no evidence of active psychosis, dementia, and/or terminal illness. Any provider responsible for direct patient care at either study site Liver Clinic will be eligible to participate in Aim 1.

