Specifically, we hypothesize that compared to patients in treatment-as-usual (TAU), participants in the web-based BAI plus TAU condition will demonstrate- **H1**: greater reductions in the number of drinking days, average drinks per drinking day, and percentage of heavy drinking days; **H2**: greater improvements in health status, psychological distress, knowledge about liver disease and alcohol use, antiviral treatment eligibility, satisfaction and perceived effectiveness with treatment; and **H3**: increased utilization of VA and non-VA outpatient SUD care at three- and six-months post-treatment.

In addition, we anticipate showing that self-directed technology can overcome traditional barriers to implementing person-delivered BAIs in liver clinics, thereby increasing Veterans' access to these services within medical settings which is a major objective of OMHS, the VA Office of Mental Health Operations (10N), and VA Office of Public Health.

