5.3 Informed Consent Procedures

Aim 1

Informed consent will be obtained verbally over the phone by the study coordinators when patients/providers call our study team in response to a study flyer. We will request a Waiver of Documentation of Informed Consent to obtain permission from patients and providers to participate in the study and to consent to audiotaping. Informed consent will be obtained before interviews are conducted by our study staff. Patients with evidence of active psychosis, dementia, and/or terminal illness will be ineligible to participate.

Aim 2

Informed consent will be obtained in written form by the study coordinators when patients are identified as possible candidates. Patients of the liver clinic indicating any use of alcohol in the prior 30-day period will be recruited to participate in this study. To enhance the generalizability of our findings, we are only excluding Veterans who are currently enrolled in an outpatient or inpatient substance abuse program. Veteran participants currently seeking other mental health care treatment will be included in this study and the details of this care will be well documented in the baseline assessment process. This will allow us to examine whether this factor moderates the effect of the study conditions on patient outcomes. Also, patients with evidence of active psychosis, dementia, and/or terminal illness will be ineligible to participate.

Aim 3

Participants who provide informed consent for Aim 2 will also be asked for permission to use their social security numbers, which addresses data access for Aim 3.

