Part III of the interview will collect data on CFIR domain C - intervention characteristics involved in the care process. Providers will be asked to give their perceptions on current guidelines for treating alcohol use in HCV clinics and availability of treatment options at their facility. For example, potential assessment domains include: (k) perceptions about existing guidelines (e.g., “What do you think about current guidelines for addressing alcohol consumption in your clinic?” and “How effective/ineffective do you feel these guidelines are in helping you address this issue in your patient population?”) and (l) perceptions about and availability of treatment options for alcohol use (e.g., “How do you feel about existing treatment options for your patients reporting active alcohol use?”). In addition, providers will be asked to provide their reactions to the following treatment options: brief physician advice, the VHA brief alcohol counseling performance measure, brief alcohol interventions (e.g., assessment and feedback [BAI]), and referral to specialty SUD care, which (along with responses to questions in Parts I-II) will inform the re-versioning of the web-based BAI.

Aim 2

Veteran participants will be randomized into the experimental condition or TAU. Participants in the experimental condition will receive a web-based BAI which follows the general approach that has proven to be effective in previous studies. The BAI consists of two components (a) a brief computerized assessment and (b) a personalized feedback report (also see section 5.1).

All participants will receive an assessment at baseline, and follow up at 3- and 6-months. The assessment consists of the following topics: demographics, liver disorder diagnosis and treatment eligibility, patient satisfaction, primary and secondary outcomes.

Assessment Instruments

(a) Demographics. Characteristic such as age, gender, and previous or current involvement with inpatient/outpatient VA (or non-VA) substance use disorder (SUD) treatment or mental health care programs will be collected from the patient and through administrative records (CPRS and CDW). We will also assess current (or past) participation in a self-help SUD program such as Alcoholics Anonymous. We will assess possible exposure to these various forms of substance abuse treatment during the three- and six-month follow up periods.

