(g) Health status. The Short Form-12 (SF-12) is a 12-item health survey based on the Medical Outcomes Study 36-item Short-Form Health Survey (SF-36) designed to assess two component health status summary scales (physical and mental component summaries) in the general U.S. population (Ware et al., 1996). The SF-12 has demonstrated good internal consistency reliability and construct validity (Luo et al., 2003).

(h) Seeking/receiving additional care. We will measure the degree to which Veteran participants seek additional SUD care over the course of the three- and six- month follow up periods. We will assess whether Veterans seek out outpatient/inpatient care of a substance abuse problem within or outside the VA system. We will also assess whether Veterans access self-help care outside the VA such as attending a meeting at Alcoholics Anonymous.

(i) Depressive symptoms. The Patient Health Questionnaire-9 (PHQ-9) is a 9-item depression scale based on the Diagnostic and Statistical Manual Fourth Edition (American Psychiatric Association, 2000). Items are scored (and summed) from 0 (not at all) to 3

(nearly every day), with severity of symptoms ranging from 0 to 27. The reliability and validity of the PHQ-9 are well established (Kroenke et al., 2001).

(j) Coping. The Coping Responses Inventory (CRI; Moos, 1993) will be used to assess participants' use of approach and avoidance coping strategies to manage stressful events (e.g., antiviral therapy). The CRI asks participants to identify their most significant stressor over the past 12 months, and then complete 48 items that describe specific coping strategies used to manage the stressor. Coping items are rated from 0 (not at all) to 3 (fairly often). The CRI comprises 8 subscales (e.g., problem solving) that have strong internal consistencies (Moos, 1993, 2002).

(k) Knowledge of HCV. This is a 16-item assessment of HCV knowledge based on patient education developed by the VA Hepatitis C Resource Center (2011). Total knowledge will be derived from percent of the questions answered correctly (ranging from 0 – 100%). Accuracy of HCV knowledge will be defined as percentage of correct answers with higher percentages reflecting more accurate HCV knowledge.

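### The SUD-treatment exclusion differs between sections, and the care outcome behind H3 is wider than H3 with no rule for care already under way at baseline, so the H3 contrast may be diluted

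*Combined protocol and SAP*

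**What the plan says.** **Eligibility.** Section 5.4 lists as a criterion "b) not presently in treatment for a substance use disorder". The Aim 2 Study Population text in Section 5.1 has the same criterion. Section 5.3 (Informed Consent Procedures, Aim 2) says instead that "we are only excluding Veterans who are currently enrolled in an outpatient or inpatient substance abuse program", and admits Veterans who are in other mental health care.

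**Baseline record.** Section 5.5, item (a) Demographics, collects "previous or current involvement with inpatient/outpatient VA (or non-VA) substance use disorder (SUD) treatment" and adds: "We will also assess current (or past) participation in a self-help SUD program such as Alcoholics Anonymous". The next sentence reads: "We will assess possible exposure to these various forms of substance abuse treatment during the three- and six-month follow up periods".

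**Hypothesis.** H3 in Section 3.0 predicts "increased utilization of VA and non-VA outpatient SUD care at three- and six-months post-treatment".

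**Outcome.** Section 5.5, secondary outcome (h), measures "the degree to which Veteran participants seek additional SUD care" over the follow-up periods. It covers outpatient and inpatient care inside or outside the VA, and then: "We will also assess whether Veterans access self-help care outside the VA such as attending a meeting at Alcoholics Anonymous".

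**Analysis.** Section 5.6 applies a generalized linear mixed model (GLMM) to primary and secondary outcomes, with terms for time, time by condition, and site. Baseline variables are added only if the arms are found to differ on them.

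**The concern.** There are two linked problems.

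First, the entry rule is not one rule. SUD medication or counselling given by a general clinician is treatment, but need not be enrolment in a program. Such a Veteran is out under Sections 5.1 and 5.4 and in under Section 5.3.

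Second, the care that excludes, the care that H3 names and the care that outcome (h) measures are three different sets. Someone who was already receiving care, was enrolled, and carries on unchanged could be recorded as having SUD care at 3 and 6 months. H3 asks whether the web-based brief alcohol intervention (BAI) leads patients to use more SUD care. Care that was going to continue anyway says nothing about that, and counting it makes a real difference in uptake harder to see.

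**Working it through.** **Step 1. Eligibility wordings side by side.**

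| Veteran's situation at entry | Sections 5.1 and 5.4 | Section 5.3 |
|---|---|---|
| Enrolled in an SUD program | Excluded | Excluded |
| SUD treatment outside a program | Excluded | Not excluded |
| Self-help only | Unclear: treatment is undefined, and Section 5.5(a) groups self-help with forms of treatment | Not stated; not excluded if the rule covers only outpatient and inpatient programs |

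The second row is a contradiction and the third a gap. The border is blurred further because Section 5.5 (Aim 1 patient interviews, Part III) gives outpatient mental health as an example of a specialty SUD program, while Section 5.3 admits patients in other mental health care.

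**Step 2. H3 against outcome (h).** H3 names outpatient SUD care, VA and non-VA. Outcome (h) adds inpatient care and self-help. The word *additional* in (h) is not defined, either relative to baseline or as first contact after randomisation.

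**Step 3. Does the planned analysis settle it?** The conditional adjustment in Section 5.6 acts only when the arms differ. Dilution occurs when they are balanced, so the trigger does not address it. A repeated-measures model with a baseline value of (h) could show continuing care at time 0. However, (h) is worded only for the follow-up periods, and no baseline score for it is defined.

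**Step 4. What carried-over care does.** Let π be the share already in care at entry who continue, and let c and b be the new-uptake rates in treatment-as-usual and BAI among the rest. If all care counts, the observed rates are

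π + (1 − π)c and π + (1 − π)b, so the difference is (1 − π)(b − c).

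If b = c, the expected difference is 0 whatever π is. If b > c, both rates rise and the difference and the ratio shrink.

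**Step 5. Illustration of size.** The plan has no figure for H3 to reproduce. Only the numbers available come from its sample size: 170 per arm × (1 − 0.20) = 136 per arm at 6 months. (The stated inputs for the drinking outcomes give 2(1.96 + 0.84)²/0.35², rounded up to 129, and 129/0.80, rounded up to 162 per arm. The 170 is slightly above this, and nothing here depends on it.)

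π, c and b are assumptions; the documents give none of them. Power is for two proportions, two-sided 0.05, with p̄ the mean of the two rates p₁ and p₂ and Δ their difference:

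Φ{[Δ − 1.96√(2p̄(1 − p̄)/n)] / √([p₁(1 − p₁) + p₂(1 − p₂)]/n)}.

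Example at π = 10%, c = 10%, b = 20%. The rates are 0.10 + 0.90 × 0.10 = 19% and 0.10 + 0.90 × 0.20 = 28%, with ratio 28/19 = 1.47. With n = 136, (0.090 − 0.1008)/0.0511 = −0.21, so power is 42%. Counting new care only, n = 136 × 0.90 = 122.4, and (0.100 − 0.0895)/0.0452 = 0.23, so power is 59%.

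| π | Observed, all care | Ratio | Power, all care | Power, new care among those without care at entry |
|---|---|---|---|---|
| 0% | 10.0% v 20.0% | 2.00 | 64% | 64% |
| 5% | 14.5% v 24.0% | 1.66 | 51% | 62% |
| 10% | 19.0% v 28.0% | 1.47 | 42% | 59% |
| 20% | 28.0% v 36.0% | 1.29 | 29% | 54% |
| 30% | 37.0% v 44.0% | 1.19 | 22% | 49% |

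Other uptake assumptions at π = 10%: for 5% v 15%, power is 47% (all care) against 74% (new care); for 15% v 30%, it is 68% against 81%.

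**Step 6. Chance imbalance.** At 170 per arm, the 95% range for the difference between arms in π is ±1.96√(2π(1 − π)/170): ±4.6 points at 5%, ±6.4 at 10% and ±8.5 at 20%. This is random and has no direction.

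**The case against.** The strongest reply has four parts.

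- *No false effect.* A reader might infer that care predating the trial would be scored as a result of the trial. The documents do not support that for the comparison of arms. Allocation is 1:1 in permuted blocks (Section 5.1), and Step 4 gives an expected difference of zero when the intervention does nothing. This part stands. The harm is limited to dilution and inflated rates within each arm.
- *Self-help attenders may not be enrolled.* A reader might also infer that the plan admits them because it records current self-help at baseline. That does not follow. The same item records current inpatient and outpatient SUD treatment, and enrolment in a program is excluded under every wording. Their status is unsettled.
- *The power figures are not the power of H3.* They assume a binary outcome that includes self-help, every carrier continuing, and no baseline value. Outcome (h) speaks of degree, and H3 of increased utilization. For outpatient care alone, dilution could come only from patients treated outside a program and admitted under Section 5.3, and that share may be small. This stands.
- *Sites need not diverge.* Section 8.0 keeps the coordinators in continuous contact, and randomisation is stratified by site. That makes divergent enrolment less likely and harmless to the balance of the arms, but does not tell either site which rule applies.

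None of this removes the conflicting criteria, the mismatch between H3 and (h), or the missing rule for continuing care.

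**Conclusion.** The point holds in a limited form. The exclusion is contradictory for treatment outside a program and silent on self-help. Outcome (h) is wider than H3 and does not separate continuing from newly started care. Carried-over care cannot be expected to produce a spurious difference between arms, but it may raise both rates and dilute the H3 contrast.

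The size is unknown. Under assumed uptake of 10% v 20%, counting all care instead of new care costs 11 points of power at π = 5% (62% to 51%) and 27 at π = 30% (49% to 22%). These are illustrations for the outcome described in Step 5. A GLMM that includes a baseline value of (h) could lose less, and H3 restricted to outpatient care could be barely affected if few patients are treated outside a program.

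H3 is a secondary hypothesis. The eligibility conflict affects who enters the whole trial, but no bias in the primary drinking comparison follows from it.

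**What to change.** 1. Reconcile Sections 5.1, 5.3 and 5.4 into one criterion that states how SUD treatment outside a program and current self-help attendance are classed. Which way each is classed is for the investigators to decide.
2. For H3, analyse outpatient SUD care as its own outcome and report self-help separately.
3. Define *additional* care, and prespecify one of two approaches: count only care newly started after randomisation, among those not receiving that type of care at entry; or adjust for baseline SUD care and self-help whether or not the arms are found to differ. If the GLMM is to do this through a baseline value of (h), say how that value is scored.

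The cost is wording in the protocol and analysis plan, because Section 5.5(a) already collects the baseline items. The new-care definition drops some participants (at π = 10%, 136 becomes about 122 per arm) and misses increased use among those already in care, which H3's wording includes. Adjustment keeps everyone, so restriction should not be the only option considered.

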5.5 Study Evaluations

Aim 1

Patient participants will be recruited by responding to a study flyer provided to them by their HCV clinic provider, or posted in an exam room or clinic research bulletin board. Eligible participants interested in the study will be asked their permission to be contacted by a study coordinator (who will also determine eligibility) to schedule an interview. All providers working in

the HCV clinics at each site will be eligible to participate.

Patient Interviews. The patient interviews will consist of open-ended questions, probing follow-up questions, and obtaining specific examples relevant to each CFIR domain. The interview will consist of three parts.

Part 1 will collect information on CFIR domain A –the outer and inner setting in which care occurs. Questions in this domain will collect information on the broader social and cultural context (outer) and more specific clinic processes (inner) that may affect the adoption of a web-based BAI as a potential intervention for Veterans with HCV and active alcohol use. Questions concerning the outer setting will focus on such factors as: (a) life circumstances (e.g., “To what extent do life circumstances influence your willingness to openly discuss alcohol use with your provider?”) and (b) involvement/impact of other people (e.g., “How do what other people think about you affect your willingness to talk about alcohol use with your provider?”). Questions concerning the inner setting will include: (c) patient centeredness of the health care setting (e.g., “To what extent to you feel the clinic in which you receive care takes your needs and preferences into account?”) and (d) access to resources (e.g., “To what extent do you feel you have access to options for supporting you in reducing your alcohol consumption?”).

Part II will collect information on CFIR domain B - the characteristics of individuals involved in the care process. Questions in this domain will assess patient and provider characteristics that may influence HCV patients’ willingness to discuss their alcohol use and receive care when appropriate. Example questions will focus on such factors as (e) communication (e.g., “Are there ways in which your provider talks to you that affects/influences your willingness to discuss alcohol use?”); (f) awareness of the consequences of drinking (e.g., “What do you know about alcohol’s effect on your health?”); (g) importance of feedback (e.g., “What type of feedback is (or was) most influential in understanding the health effects of drinking?”); (h) decision to change (e.g., “To what extent does changing your eligibility for antiviral treatment impact your interest in seeking care for your alcohol use?”); and (i) readiness to use a web-based BAI (e.g., “Describe your degree of openness to interacting with a BAI delivered by the internet.”, “What factors influence your interest/willingness to interact with a self-administered BAI?”).

Part III will focus on CFIR domain C - intervention characteristics involved in the care process. Patient participants will be presented content from several evidence-based approaches for addressing alcohol use including: (a) brief advice, (b) brief alcohol counseling (e.g., VHA brief alcohol counseling performance measure), (c) brief alcohol interventions (e.g., assessment and feedback [BAI]), and (d) referral to specialty SUD care. Patient participants will be asked for feedback and reactions to the content of these care strategies, their format, and general presentation. If participants have been exposed to these approaches before in their interactions with providers, they will be asked for their reactions to and experiences with them. Patient feedback on these care strategies (and responses to questions in Parts I-II) will be used to help inform the re-versioning of the web-based BAI. For example, these interviews may yield rich information regarding patient preferences on types of specialty SUD programs (e.g., outpatient mental health) and approaches to the referral process (e.g., direct provider prescription, preference for the “hallway handoff”) that will inform the manner in which we integrate this information into the web-based BAI.

Provider Interviews. Provider interviews will follow the same general strategy as the patient interviews with question development guided by both the findings of Michie et al. (2005) and Felker et al. (2006) describing factors critical in providers’ adoption of innovative, evidence-based health care practices

Part 1 will consist of open-ended questions that gather information on CFIR domain A- the outer

and inner setting in which care occurs. Questions will gather data on the outer setting by examining topics such as (a) policy factors that may influence care (e.g., “How do patient/provider ratios impact your ability to provide counseling to HCV-positive patients with active alcohol use?, What impact does your clinic policy for responding to active alcohol use have on your ability to counsel HCV-positive patients?) and (b) social influences (e.g., “To what extent do social influences [peers or managers] facilitate or hinder open discussion of alcohol use with your patients?). Questions concerning the inner setting will assess such factors as (c) the clinic environment and available resources (e.g., “To what extent do physical or other resource factors facilitate or hinder your ability to have open discussions of alcohol use with your patients?”) and (d) availability of time (e.g., “What preparatory steps are needed to provide effective counseling for alcohol use in this population?”).

Part II will collect information on CFIR domain B - the characteristics of individuals involved in the care process, including providers’ knowledge (e.g., “What do you know about the guidelines for screening and treating alcohol use in Veterans with HCV?”) (f) skills (e.g., “To what extent do you feel like you have sufficient skill to identify active alcohol use with your patients?”); (g) beliefs about their own capabilities (e.g., “What do you think will happen if you provide alcohol counseling to a patient?”); (h) motivation and goals (e.g., “How much do you want to provide alcohol counseling [or referral to a web-based BAI] when indicated?”); (i) memory, attention, and decision process (e.g., “Describe any situations in which you chose not to provide alcohol counseling in response to active alcohol consumption.”, “To what extent would an alternative to provider-delivered counseling, such as a self-administered BAI, help support you in addressing alcohol use in your patients?”); (j) emotions (e.g., “To what extent do emotional factors facilitate or hinder open discussion of alcohol use with your patients?”) and (k) readiness to adopt a web-based BAI (e.g., “Describe your level of interest/willingness to recommend a web-based BAI to patients reporting active alcohol use.” , “Describe your clinics level of readiness to adopt a web-based BAI as a potential intervention for reducing alcohol consumption” .).

Part III of the interview will collect data on CFIR domain C - intervention characteristics involved in the care process. Providers will be asked to give their perceptions on current guidelines for treating alcohol use in HCV clinics and availability of treatment options at their facility. For example, potential assessment domains include: (k) perceptions about existing guidelines (e.g., “What do you think about current guidelines for addressing alcohol consumption in your clinic?” and “How effective/ineffective do you feel these guidelines are in helping you address this issue in your patient population?”) and (l) perceptions about and availability of treatment options for alcohol use (e.g., “How do you feel about existing treatment options for your patients reporting active alcohol use?”). In addition, providers will be asked to provide their reactions to the following treatment options: brief physician advice, the VHA brief alcohol counseling performance measure, brief alcohol interventions (e.g., assessment and feedback [BAI]), and referral to specialty SUD care, which (along with responses to questions in Parts I-II) will inform the re-versioning of the web-based BAI.

Aim 2

Veteran participants will be randomized into the experimental condition or TAU. Participants in the experimental condition will receive a web-based BAI which follows the general approach that has proven to be effective in previous studies. The BAI consists of two components (a) a brief computerized assessment and (b) a personalized feedback report (also see section 5.1).

All participants will receive an assessment at baseline, and follow up at 3- and 6-months. The assessment consists of the following topics: demographics, liver disorder diagnosis and treatment eligibility, patient satisfaction, primary and secondary outcomes.

Assessment Instruments

(a) Demographics. Characteristic such as age, gender, and previous or current involvement with inpatient/outpatient VA (or non-VA) substance use disorder (SUD) treatment or mental health care programs will be collected from the patient and through administrative records (CPRS and CDW). We will also assess current (or past) participation in a self-help SUD program such as Alcoholics Anonymous. We will assess possible exposure to these various forms of substance abuse treatment during the three- and six-month follow up periods.

(c) Patient satisfaction. We will use a brief patient survey that we developed from our preliminary work to assess patients' satisfaction with both treatment conditions. This survey will ask patients to respond to a series of statements regarding their satisfaction with the interventions received (e.g., "I felt comfortable disclosing my alcohol use to a computer program"; "My provider helped me understand how alcohol use may worsen liver disorder(s)."). This assessment will be completed by patients upon completion of the baseline assessment (and upon completion of the web-based BAI for patients assigned to the experimental condition).

Primary Outcomes.

(d) Alcohol quantity and frequency. Reduction in alcohol use will be measured using the 30-day Time Line Follow-Back instrument (TLFB; Sobell & Sobell, 1992). The TLFB is a calendar that provides visual cues to aid persons in retrospective recall of drinking behavior. It uses "cues" (e.g., holidays, birthdays) to help a participant recall drinking behavior (e.g., frequency and quantity of alcohol use) and has been shown to be reliable and accurate when administered individually over the telephone (Sobell et al., 1996). Based on recommendations from the alcohol treatment literature we will assess the *(a) number of drinking days, (b) mean number of drinks per drinking day, and (c) percentage of heavy drinking days* in the prior 30 days as our primary outcomes (Dieperink et al., 2010; Gastfriend et al., 2007). These outcomes will be measured by comparing TLFB drinking data at baseline (30-days prior) to data collected at three- and six-month follow-up (30 days prior).

Secondary Outcomes.

(e) Consequences of alcohol use. The Short Index of Problems (SIP-3months) is a brief, 15-item version of the Drinker Inventory of Consequences (DrInC) which assesses alcohol-related problems over the prior 3-months (Woolard et al., 2004). The SIP has sound psychometric properties (Kenna et al., 2005).

(f) Symptoms of psychological distress. Symptoms of psychological distress will be measured using the Brief Symptoms Inventory (BSI). The BSI instrument provides an overview of a patient's symptoms and their intensity at a specific point in time (Derogatis & Melisaratos, 1983). The reliability, validity, and clinical utility of the BSI instrument are well-established.

(g) Health status. The Short Form-12 (SF-12) is a 12-item health survey based on the Medical Outcomes Study 36-item Short-Form Health Survey (SF-36) designed to assess two component health status summary scales (physical and mental component summaries) in the general U.S. population (Ware et al., 1996). The SF-12 has demonstrated good internal consistency reliability and construct validity (Luo et al., 2003).

(h) Seeking/receiving additional care. We will measure the degree to which Veteran participants seek additional SUD care over the course of the three- and six- month follow up periods. We will assess whether Veterans seek out outpatient/inpatient care of a substance abuse problem within or outside the VA system. We will also assess whether Veterans access self-help care outside the VA such as attending a meeting at Alcoholics Anonymous.

(i) Depressive symptoms. The Patient Health Questionnaire-9 (PHQ-9) is a 9-item depression scale based on the Diagnostic and Statistical Manual Fourth Edition (American Psychiatric Association, 2000). Items are scored (and summed) from 0 (not at all) to 3

(nearly every day), with severity of symptoms ranging from 0 to 27. The reliability and validity of the PHQ-9 are well established (Kroenke et al., 2001).

(j) Coping. The Coping Responses Inventory (CRI; Moos, 1993) will be used to assess participants' use of approach and avoidance coping strategies to manage stressful events (e.g., antiviral therapy). The CRI asks participants to identify their most significant stressor over the past 12 months, and then complete 48 items that describe specific coping strategies used to manage the stressor. Coping items are rated from 0 (not at all) to 3 (fairly often). The CRI comprises 8 subscales (e.g., problem solving) that have strong internal consistencies (Moos, 1993, 2002).

(k) Knowledge of HCV. This is a 16-item assessment of HCV knowledge based on patient education developed by the VA Hepatitis C Resource Center (2011). Total knowledge will be derived from percent of the questions answered correctly (ranging from 0 – 100%). Accuracy of HCV knowledge will be defined as percentage of correct answers with higher percentages reflecting more accurate HCV knowledge.

(l) Social norms. Two questions will assess perceived quantity and frequency of alcohol consumption among participants' peers (i.e., descriptive norms, e.g., "How many drinks on one occasion do men/women your age consume?" [frequency]), while a 10-item measure will be used to assess concerns about harmful alcohol use (injunctive norms; Williams et al., 2009).

(m) Mini International Neuropsychiatric Interview (MINI). Section J, Alcohol Abuse and Dependence will measure the level of alcohol consumption over the past 30 days among participants. This is a 12-item assessment, with items rated from 0 (not at all) to 4 (extremely). This questionnaire will assess the presence of an alcohol use disorder (AUD) among participants.

Formative Evaluation Plan

We will utilize a well-established formative evaluation protocol that will include two site visits (to each study site) and interviews with staff (at each site) at three-month post initial implementation (e.g., Curran et al., 2008).

At the first site visit study staff will spend a day in each clinic reading program policy manuals and meeting with clinic directors. The latter will provide an opportunity to pose more focused questions on clinic policies (especially related to screening and treating current alcohol use). The meetings will be used to gauge clinic directors' support for the project as initial implementation will occur approximately one-year after funding notification. Therefore, it will be important to reassess clinic directors' current attitudes and beliefs, and answer any questions on the implementation process. When necessary we will provide brief, evidence summaries on the effectiveness of web-based BAIs and advocate VA practice guidelines for screening and treating alcohol use or misuse when appropriate.

For the second site visit, approximately three-months after the initial visit (and post-implementation), Co-Investigator ([name]) and site coordinator will complete a second three-day visit to each study site. This second visit will include observations of program operations and conducting interviews with clinic staff. First, we will conduct observations that will focus on clinic policies, norms, and staff-patient relationships (especially related to screening and treating current alcohol use and use of the web-based BAI). Observations will be both formal and informal. The former will consist of "scheduled" observations where the Co-I or study coordinator will observe intake interviews, screening efforts for alcohol use, educational presentations, and referral of patients reporting current alcohol use to the web-based BAI.

Study staff will also perform informal observations of patient flow, and staff and staff-patient relationships in central clinic locations (e.g., nurses' station). Second, we will conduct interviews with 10 clinic staff members (5 at each study site) that help us identify possible barriers and facilitators to the sustained adoption of the web-based BAI at both study clinics. The study coordinators will conduct these interviews with providers (N = 10) following the same general recruitment and interview approach as outlined in Aim 1.

Aim 3

With consent, the study will collect the patient's social security number. We will link the social security number to the VA scrambled social security number so that we can extract their VA utilization and cost data. We will collect utilization and cost data from randomization through one year for each participant. Data will be gathered from a variety of sources.

OMHO will provide our team with a subset of a larger OMHO global data set that includes VA SUD patient level utilization data. In doing so, they will effectively be contributing staff time of two FTE data analysts for years 3 and 4 whose job is to develop these global data sets. This contributed work overlaps existing program evaluation and quality improvement efforts regularly conducted by OMHO. This will reduce the need to pay for analysts for this project.

(a) VA Utilization Data. The Office of Mental Health Operations (OMHO) uses the VA National Patient Care Database and the Patient Treatment Files (PTF), and Decision Support System Files (DSS) to characterize quantity and type of SUD and mental health care received by individual VA patients. The OMHO databases include information on number of outpatient visits, residential care received, pharmacotherapy, psychoeducation and psychotherapy receipt, and use of detoxification services. OMHO will provide the project team with utilization data for patients included in the effectiveness study (i.e., Aim 2).

(b) VA Cost Data. Using the DSS, OMHO will provide costs associated with each of the care elements described in the utilization data sets.

(c) Non-VA Care-Utilization and Cost Data (paid for by VA). Because VA patients may obtain approved health care outside the VA system during the study period, the cost of such care must be taken into account. We will use the Fee Basis file to capture all care provided outside the VA and paid for by VA.

